#### Unscheduled Measurements

Unscheduled measurements will be included in the listings. Except for unscheduled measurements used for baseline, unscheduled measurements will be excluded from the descriptive statistics and statistical analysis.

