3.4.3 Safety Outcome Measures

The safety outcome measures for this study are as follows:

- Incidence, nature, and intensity of adverse events
- Incidence and nature of laboratory abnormalities, based on hematology, clinical chemistry, [REDACTED], coagulation monitoring, and urinalysis testing
- Tanner staging (see [Appendix 6](#))
- Physical examination (including body height and weight) and neurological examination (see [Appendix 5](#))
- Vital signs, i.e., systolic and diastolic blood pressure, pulse rate in supine position, and orthostatic hypotension
- Frequency of body temperature exceeding 38°C (100.4°F) lasting for longer than 1 hour differentiated according to whether or not this presents with an absolute neutrophil count (ANC) below 1,000/μL (confirmed)

[REDACTED]

- Suicidality evaluated by the Columbia-Suicide Severity Rating Scale (C-SSRS) or as evaluated by dedicated questions on suicidal ideation and behavior or as reported through AE

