4.6.1.7 Laboratory Assessments

Normal ranges for the study laboratory parameters, by age and sex where appropriate, must be supplied to the Sponsor before relevant assessments are completed.

Laboratory safety tests shall be collected at time-points specified in the Schedule of Assessments ([Appendix 1](#), [Appendix 2](#), [Appendix 9](#), and [Appendix 10](#)).

Additional blood or urine samples may be taken at the discretion of the Investigator if the results of any test fall outside the reference ranges, or clinical symptoms necessitate

additional testing to monitor subject safety. Where the clinical significance of abnormal lab results is considered uncertain, screening lab tests may be repeated before randomization to confirm eligibility. If there is an alternative explanation for a positive urine or blood test for drugs of abuse, e.g., previous occasional intake of a medication or food containing for example codeine, benzodiazepines or opiates, the test could be repeated to confirm washout.

In the event of unexplained abnormal clinically significant laboratory test values, the tests should be repeated immediately and followed up until they have returned to the normal range and/or an adequate explanation of the abnormality is found. [REDACTED]

[REDACTED] Results of clinical laboratory testing will be recorded on the eCRF or be received as electronically produced laboratory reports submitted directly from the local or central laboratory, if applicable.

- Hematology: leukocytes, erythrocytes, hemoglobin, hematocrit, platelets, differential count [neutrophils, eosinophils, basophils, monocytes, lymphocytes, other cells]. Additional hematology monitoring will be performed at so called “home visits” ([Appendix 1](#), [Appendix 2](#), [Appendix 9](#), [Appendix 10](#), and [Section 5.2.1](#)).
- Serum chemistry:
As specified in the schedule of assessments (see [Appendix 1](#), [Appendix 2](#), [Appendix 9](#), and [Appendix 10](#)), different serum chemistry assessments will be performed at specific visits:
 - Full Serum chemistry panel: sodium, potassium, chloride, bicarbonate, glucose (fasting for at least 4 hours at screening only), urea, creatinine, phosphate, calcium, total and direct bilirubin, alkaline phosphatase, ALT, AST, protein, albumin, urate, LDH, CPK, total cholesterol, LDL cholesterol, HDL cholesterol, triglycerides.

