Additionally, HbA1c, TSH, and free T4 will be assessed at screening, Week 24/76 early withdrawal, and 6-week follow-up visits.

[REDACTED]

[REDACTED]

[REDACTED]

[REDACTED]

- Coagulation: INR, aPTT, PT

- Viral serology:
 - HIV (specific tests HIV-1 Antibody, HIV-1/2 Antibody, HIV-2 Antibody)
 - Hepatitis B surface antigen (HBsAg) *or hepatitis B cDNA*
 - Total hepatitis B core antibody (HBcAb)
 - *Any positive HBV serology will be followed by confirmatory assays.*
 - Hepatitis C virus (HCV) antibody
- Urinalysis, including dipstick: pH, specific gravity, glucose, protein, ketones, blood will be performed at the study center. If there is a clinically significant positive blood or protein result, urine will be sent to the central laboratory for microscopy and culture.
- Urine Drug Screen and alcohol test: Urine samples will be analyzed for the presence of the following drugs: alcohol, cannabinoids, opiates, methadone, cocaine, and PCP. Drug screen and alcohol test will be mandatory for adolescents at screening and may be performed in any subject at any visit at the discretion of the study physician.
- Pregnancy test: All females with menarche (including those who have had a tubal ligation) will have a urine pregnancy test at screening and specified sub-sequent visits.
- Unscheduled Visit: In the event that additional laboratory parameters are required to interpret any adverse events or abnormal hematology/chemistry, the following assessments may be included:
 - Hematology: leukocytes, erythrocytes, hemoglobin, hematocrit, platelets, differential count (neutrophils, eosinophils, basophils, monocytes, lymphocytes, other cells)
 - Full serum chemistry panel: sodium, potassium, chloride, bicarbonate, glucose (fasting for at least 4 hours at screening only), urea, creatinine, phosphate, calcium, total and direct bilirubin, alkaline phosphatase, ALT, AST, protein, albumin, urate, LDH, CPK, total cholesterol, LDL cholesterol, HDL cholesterol, triglycerides

[REDACTED]

[REDACTED]

[REDACTED]

[REDACTED]

[REDACTED]

[REDACTED]

[REDACTED]

[REDACTED]

The procedures for the collection, handling, and shipping of samples will be provided in the Central Laboratory Manual.

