### 3.3 TIME-WINDOWS

Efficacy and safety analyses will be performed according to the data collected at the originally scheduled visit.

In case of deviations from the visit date scheduled as per protocol the following boundaries will be implemented to identify time-windows:

| Site Visit | Time-window (days)                | Range (days)  |
|------------|-----------------------------------|---|
| Baseline   | Before or soon after Start Dosing | Up to the 1 st day of dosing                                       |
| Week 6     | 43 ± 21                           | 23 – 64   |
| Week 12    | 85 ± 21                           | 65 – 106  |
| Week 18    | 127 ± 21                          | 107 – 148   |
| Week 24    | 169 ± 21                          | 149 – at most 21 days after last double-blind Dose and prior to OLE Screening |

For Screening, the scheduled visit will be used regardless of the actual assessment days relative to the first day of study drug.

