### **4.6 SAFETY ANALYSES**

Summary tables and graphs will be provided both for the “Safety Global” and for the “Safety Inferential” populations, while listings of individual data will be provided for the “Safety Global” population only, separately by subjects’ patterns (a, b, c, d).

As appropriate, listings, summary tables and graphs by treatment group will be provided for safety and tolerability assessments, including:

- Incidence of adverse events (overall, by intensity, and by relationship to study medication).

- Serious adverse events and adverse events of special interest will be reported separately.
- [REDACTED]
- Vital signs (systolic blood pressure, diastolic blood pressure, pulse rate, and orthostatic effects)
- [REDACTED]
- Physical examination (height, weight, neurological examination)
- Safety laboratory values (including hematology, blood chemistry, coagulation, and urinalysis parameters)
- Incidence of marked laboratory abnormalities
- Clinical assessment of suicidality (C-SSRS)

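### Read as written, SAP 3.3 leaves post-baseline unscheduled laboratory values out of the incidence of marked abnormalities, so that table is understated by an amount that cannot be estimated

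*SAP*

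**What the plan says.** SAP 3.3 (Time-Windows) opens by setting its scope: "Efficacy and safety analyses will be performed according to the data collected at the originally scheduled visit". Under its Unscheduled Measurements heading it makes three statements:

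- "Unscheduled measurements will be included in the listings".
- One exception is given: "Except for unscheduled measurements used for baseline".
- All other "unscheduled measurements will be excluded from the descriptive statistics and statistical analysis".

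SAP 4.6 then plans, among its listings, tables and graphs by treatment group, "Incidence of marked laboratory abnormalities". The Clinical Laboratory text in the same section defines a marked abnormality as a value beyond Roche's marked range that also shows a defined change from baseline. Protocol 6.5.2.2 gives the same definition. Neither says whether unscheduled values qualify.

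Protocol 4.6.1.7 expects off-schedule sampling. When a clinically significant result is unexplained, "the tests should be repeated immediately and followed up until they have returned to the normal range" or an explanation is found. Haematology and a full chemistry panel may be added at an unscheduled visit: "In the event that additional laboratory parameters are required to interpret any adverse events or abnormal hematology/chemistry". Protocol 3.4.3 also has a fever outcome, split by whether or not "this presents with an absolute neutrophil count (ANC) below 1,000/μL (confirmed").

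**The concern.** Leaving unscheduled values out of by-visit means and repeated-measures models is ordinary practice, because it stops subjects with problems from contributing extra observations to a visit. An incidence table answers a different question: did this subject have a marked abnormality at any time after baseline? Samples drawn because something appeared to be wrong are among the most informative for that question, and the rule as worded sends them to the listings only.

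At stake is the one predefined laboratory measure of harm that is compared by arm and does not depend on investigator judgement. Safety and tolerability is a secondary objective of this paediatric study. The efficacy conclusions are not affected.

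**Working it through.** The plan states no figure on this point, so the check is mainly a reading of the sections together.

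1. **Does the rule reach safety data?** Yes. The first sentence of SAP 3.3 names both efficacy and safety analyses.
2. **Which unscheduled values escape it?** Only those used as baseline. Every post-baseline unscheduled value is caught.
3. **Is the incidence table a descriptive statistic?** In the ordinary sense it is: a count and percentage by treatment group. SAP 4.6 does not say that it falls outside the rule.
4. **Does any later text restore the values?** The marked-abnormality definitions (SAP Clinical Laboratory; Protocol 6.5.2.2) contain no clause for any post-baseline value or the worst value. The visible parts of Protocol 6.5 contain neither the exclusion nor an exception to it.
5. **Does the protocol generate such values?** Yes, by both routes in Protocol 4.6.1.7: repeats of abnormal results, and samples taken to interpret events.
6. **Which values are lost from the table?** The definition requires no confirmation, so a marked value at a scheduled visit counts whether or not it is repeated. The loss is confined to abnormalities first or only seen on an unscheduled sample. If the first sighting is unscheduled and a later scheduled value is also marked, the subject is still counted.
7. **Are home-visit samples lost?** No. The Week 4, 8, 16 and 20 draws are part of the Appendix 1 schedule.
8. **Fever outcome.** Fever does not follow the visit calendar, so the neutrophil count or its confirmation may be unscheduled. If so, the same rule would drop it. The visible SAP text does not say how this outcome is summarised.

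**Form of the understatement.** Let p be the true proportion of subjects with a marked abnormality that was sampled at some point, and u the share of those subjects whose abnormality was seen only on unscheduled samples. The table then shows p × (1 − u). If u is the same in both arms, the difference in proportions shrinks by the factor (1 − u) and the ratio is unchanged. If u differs between arms, the ratio changes too.

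The documents give neither p nor u. Purely to show the scale in counts, assume p of 2% to 10% and u of 10% to 50%, with 80 subjects per arm (the planned evaluable number):

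- p = 2%: 80 × 0.02 = 1.6 subjects. The table shows 1.6 × 0.9 = 1.4 down to 1.6 × 0.5 = 0.8.
- p = 10%: 80 × 0.10 = 8.0 subjects. The table shows 8.0 × 0.9 = 7.2 down to 8.0 × 0.5 = 4.0.

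These values of p and u are assumptions, not estimates for this trial.

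**The case against.** **The rule may be aimed only at by-visit statistics.** It sits under time-windows, and the natural target of the exclusion is the laboratory summary at each assessment time. The marked-abnormality definition speaks of values without limiting them to scheduled ones, so a programmer could count all of them. This stands in part: the consequence follows from a general rule that is not repeated beside the table. But the rule names safety, gives a single exception, and is the only text that addresses the question. If two programmers could build different tables from it, the SAP needs to say which is meant.

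**Other outputs catch much of the loss.** This stands. Unscheduled values remain in listings, where marked abnormalities carry HH or LL labels. Under Protocol 5.3.5.4 a laboratory result becomes a reportable adverse event if it has symptoms, changes treatment, leads to intervention or is judged clinically significant, and adverse events are tabulated without a scheduled-visit limit. Raised ALT or AST with raised bilirubin or jaundice must be reported at once (Protocol 5.3.5.6). A symptom-triggered abnormality will often enter by one of these routes. These routes do not repair the marked-abnormality table itself: listings give no between-arm comparison, and adverse-event reporting rests partly on judgement.

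**Stronger readings that a reader might infer, and that the documents do not support:**

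- *Confirmatory repeats are lost from the incidence table.* They are not needed there, because the definition requires no confirmation.
- *The fever outcome cannot be derived.* Some counts may fall on scheduled draws. The haematology follow-up that Protocol 4.6.1.7 refers to Section 5.2.1 is redacted, as are some safety-output bullets. Only a possible loss can be shown.
- *The gaps in the schedule measure the loss.* A draw every 28 days meets 7/28 = 25% of 7-day episodes with random onset, and full chemistry 84 days apart meets 7/84 = 8%. That describes sparse sampling. It equals the loss from the table only if every missed episode was caught by an unscheduled sample, for which the documents give no figure. CPK is also drawn at least four-weekly, early-withdrawal and follow-up draws are scheduled, and part of the chemistry text is redacted.
- *Worst-value tables for ECG and vital signs are distorted.* The SAP plans raw values and changes by time for these, so there is no such table to distort.

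**Conclusion.** The concern holds for one output. Read as written, SAP 3.3 keeps marked laboratory abnormalities first or only seen on unscheduled samples out of the by-treatment incidence table, and that incidence is understated wherever such cases occur. The size cannot be estimated from the documents. A reader might infer that the trial's whole safety comparison is biased towards no difference. That goes too far, because the adverse-event tables and listings are untouched by the rule's exclusion, and with equal proportional loss in both arms the ratio is preserved.

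The possible effect on the fever outcome is secondary and conditional on the confirming count being unscheduled. The conclusion assumes that an incidence is a descriptive statistic within the meaning of SAP 3.3, and that no redacted passage contains an exception. It should be corrected before the tables are programmed: the rule is explicit and the remedy is cheap.

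**What to change.** Amend SAP 3.3 so that the exclusion of unscheduled measurements applies to by-visit summaries and to the repeated-measures and logistic models only. Add, in SAP 4.6, that all post-baseline values, scheduled or unscheduled, within the on-treatment and follow-up period count towards the incidence of marked laboratory abnormalities and towards the fever outcome with confirmed neutrophil count. Name the period. Subjects who go straight into the open-label extension have their follow-up visit deferred to the end of that phase, so the text should say where the double-blind count stops for them.

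No new data and no new worst-value tables for ECG or vital signs are needed. The cost is a few sentences and minor programming. The downside is that reported incidences may be slightly higher, which is the purpose of the change.

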## 4 STATISTICAL METHODS

### 4.1 ANALYSIS DATASETS

According to the protocol, the disposition of subjects in relationship with each Study Part may be as follows:

**Table 4. Patterns of subjects' disposition**

| Pattern | Description: Subjects ...   | First Part
(Study part 1):
up to 8 weeks
of Treatment | Main Part
(Study part 2):
24 weeks of
Treatment |
|---------|---|--|--|
| a)      | stopped treatment prior to determination of final doses by IMC/SOC  |  |  |
| b)      | stopped treatment prior to determination of final doses by the IMC/SOC and took the opportunity to restart in the Main Part |  |  |
| c)      | allowed by the IMC/SOC to continue and complete the 24 weeks of treatment without dose interruption/adjustment              |  |  |
| d)      | enrolled in the Main Part   |  |  |

The primary **Efficacy** treatment comparison (balovaptan 10 mg equivalent dose vs. placebo) will be performed on the dataset obtained by pooling data from patients that were expected to take treatment for 24 weeks, as described by patterns c) and d) [highlighted in yellow].

**Safety** analysis will be performed separately on two datasets, according to the duration of the seamless treatment period that subjects have been exposed to. Therefore, two safety analysis datasets are identified:

- **First Part (8 weeks)** - Data from subjects that took treatment up to a maximum of 8 weeks, as described in pattern a) and 1st part of b) [framed with dotted red line]
- **Main Part (24 weeks)** - Data from subjects that took treatment up to a maximum of 24 weeks, as described in pattern c), d), and 2nd part of b) [framed with dotted blue line]

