6.3.3 Efficacy Analysis Population

6.3.3.1 *For All Subjects Enrolled prior to Version 6 of the Protocol:* **Modified Intent-To-Treat Population**

The modified intent-to-treat (mITT) population is defined as consisting of all subjects who give informed consent, are randomized, received at least one dose of double-blind medication, and for whom a baseline and at least one post-dose assessment is available. Subjects in first adolescent/first children cohorts with dose adjustments, or who were on a different dose than the final dose for their age group, will be excluded from the primary efficacy analysis, and will not contribute to the approximately 160 evaluable subjects expected in the mITT population (see Section 4.2.1). Data will be analyzed according to the treatment as randomized.

The mITT population is the primary population of interest.

Per-Protocol Population

The Per-Protocol (PP) population will be precisely defined in the statistical analysis plan, which will be finalized before database closure, as the subset of the mITT population without major protocol deviations.

The PP population will not be analyzed if this population comprises more than 90% or less than 50% of the mITT population. Only the key efficacy outcome measures (see Section 3.4.1) will be analyzed using the PP population.

6.3.3.2 *For Subjects Enrolled in Accordance to Version 6 of the Protocol:*

Intent-To-Treat Population

The intent-to-treat (ITT) population is defined as consisting of all subjects who give informed consent, are randomized, and receive at least one dose of double-blind medication. Subjects with dose adjustments or interruptions, or who were on a different dose than the final dose for their age group, will be excluded from the primary efficacy analysis and will not contribute to the approximately 160 evaluable subjects expected after 24 weeks. Data will be analyzed according to the treatment as randomized.

The ITT population is the primary and the population assessed for efficacy.

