### **2.3 DETERMINATION OF SAMPLE SIZE**

Prior to protocol version 6, a sample size of 240 subjects with ASD (80 per treatment arm) providing evaluable data at Week 24 ensured the study 80% power to detect as statistically significant, at 1-sided 5% significance level, a difference between each active dose and placebo with an effect size of at least 0.4. For the Vineland™-II 2DC score, assuming a standard deviation of about 12.5 points, then the effect size of 0.4 corresponds to 5 points. No adjustment for multiple doses was performed. Considering a withdrawal rate of around 15-20%, it was planned to recruit approximately 300 subjects overall.

In accordance to protocol version 6, 80 subjects per treatment arm (balovaptan 10 mg equivalent and placebo) are required, for a total sample size of approximately 160 subjects with ASD with evaluable data at Week 24. To achieve this number of evaluable subjects, the overall sample size in the study since it started is expected to increase to approximately 340 subjects.

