#### **4.3 ANALYSIS OF STUDY CONDUCT**

The number of subjects who enroll, discontinue or complete the study will be summarized for the Safety population/dataset by treatment group. Reasons for premature withdrawal from the study and premature withdrawal from treatment will be listed and summarized.

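### First-cohort subjects on the final dose or concurrent placebo who withdraw before dose determination fall outside both Inferential sets, although no dose-based exclusion covers them

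*SAP*

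**What the plan says.** SAP Table 4 sorts subjects into four patterns. Pattern a is those who "stopped treatment prior to determination of final doses by IMC/SOC". Pattern b is the same group when they later restarted in the Main Part. Pattern c is first-cohort subjects whom the committees (IMC/SOC) allowed to go on, and pattern d is subjects enrolled directly into the Main Part. Neither a nor b states a reason for stopping or a dose condition.

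The First Part safety dataset is "Data from subjects that took treatment up to a maximum of 8 weeks, as described in pattern a", together with the first period of b. The Main Part is the second period of b plus c plus d. Table 5 gives both Inferential sets as c + d, and Efficacy ITT Global as the second period of b plus c plus d, with nothing from the First Part.

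The exclusions written in words are about dose. Protocol 6.3.3.1 removes "Subjects in first adolescent/first children cohorts with dose adjustments, or who were on a different dose than the final dose for their age group". SAP 4.2.2 removes subjects with dose adjustments, interruptions or a non-final dose. The same section defines the Global efficacy population as everyone dosed, prematurely withdrawn or not.

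On disposition, SAP 4.3 states: "The number of subjects who enroll, discontinue or complete the study will be summarized for the Safety population/dataset by treatment group".

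**The concern.** Take a first-cohort subject on placebo, or aged 15–17 on 10 mg, who leaves at Week 5 because of an adverse event. The dose is the final dose for that age, so neither dose-based exclusion applies. Table 5 still keeps the subject out of both Inferential sets, because membership of c requires having been cleared to continue. A pattern d subject who leaves at Week 5 for the same reason is in both.

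Membership is thus conditioned on a post-baseline outcome, staying on treatment, for one recruitment block only. Pattern c subjects cannot contribute a withdrawal before clearance, yet their early weeks count in the Main Part.

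What is at stake is mainly safety. Safety Inferential is the only planned safety summary that sets 10 mg equivalent against placebo (SAP 4.2.1; Safety Global is summarised by exposure tertile), and it is also used at the interim analysis (SAP 4.5.2). Early withdrawals from the first cohorts are missing from it.

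**Working it through.** **1. The plan's design figure.** Inputs from SAP 2.3: the test level and effect are stated as "at 1-sided 5% significance level, a difference between each active dose and placebo with an effect size of at least 0.4"; the target power is 80%; the spread is given by "assuming a standard deviation of about 12.5 points"; and the number needed is that "80 subjects per treatment arm (balovaptan 10 mg equivalent and placebo) are required". An effect of 0.4 × 12.5 = 5 points needs n = 2(1.645 + 0.842)² / 0.4² = 77.3, so 78 per arm, against 80 stated. Power at 80 per arm is Φ(0.4 × √(80/2) − 1.645) = 0.812. The figure reproduces. Restoring the omitted subjects does not change it, because they have no Week 24 data.

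**2. Where the example subject goes.** The subject is in the first cohort, on the final dose or concurrent placebo, and withdrew before dose determination.

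| Set | Text definition | Table 5 |
|---|---|---|
| Safety Global | in | First Part, if pattern a |
| Efficacy ITT Global | in (all dosed) | out |
| Efficacy ITT Inferential | not caught by the dose rule, but not c or d | out |
| Safety Inferential | same subset as the primary efficacy set | out |

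If pattern a means only committee-directed stops, the subject fits no pattern and is still outside c + d. Permanent withdrawal cannot sensibly be called a dose interruption under SAP 4.2.2, since that would also remove every pattern d withdrawer.

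**3. How many subjects are eligible.** The first adolescent cohort is about 24, randomised 1:1:1, so 8 per arm and 16 on active drug. Protocol 4.3 places 10 active subjects in the 13–14 age band, leaving 16 − 10 = 6 active aged 15–17, about 3 of them on 10 mg. Starting doses were later changed for ages 5–14, so only the 15–17 band began on the final 10 mg equivalent dose.
- Lower count: 3 on 10 mg plus placebo aged 15–17, 8 × 6/16 = 3, giving 6.
- Upper count: 3 on 10 mg plus all first-cohort placebo, 8 adolescents and 30/3 = 10 children, giving 21.

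Which early placebo subjects count depends on the highlighting in SAP Table 3, which is not visible in the text; hence the range.

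**4. Expected number omitted.** Assume the planned withdrawal W over 24 weeks has constant hazard and that the First Part lasts 8 weeks: w = 1 − (1 − W)^(8/24).

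| W | w by Week 8 | 6 eligible | 21 eligible |
|---|---|---|---|
| 15% | 5.3% | 0.32 | 1.11 |
| 20% | 7.2% | 0.43 | 1.51 |

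The chance of at least one such subject, 1 − (1 − w)^n, is 28–36% with 6 eligible and 68–79% with 21.

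**5. Which endpoints could change.** Vineland-II is first repeated at Week 12 (Protocol Appendix 1), and Appendix 2 shows none at the first-cohort End of Treatment visit. The omitted subjects would normally have no post-baseline 2DC value. ABC and RBS-R are collected at Week 6 and at End of Treatment in Appendix 2, and SAP 4.5 analyses both by MMRM, so some usable data can be lost there.

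**The case against.** Several stronger readings are tempting, and the documents do not support them.

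- **Pattern a covers stops for any reason.** The SAP does not say so. Near-identical wording in Protocol 3.1.1, and the restart footnote in Appendix 1, describe subjects stopped in the context of the dose decision. That may well be the intended meaning. The gap remains, because the SAP then gives an own-reason withdrawer no pattern.
- **The protocol excludes first-cohort subjects for dose reasons only.** Protocol 6.3.3.1 also required a baseline and at least one post-dose assessment for the mITT population. A subject leaving very early might fail that condition.
- **Three or four subjects are lost.** Applying 5.3–7.2% to all 54 planned first-cohort subjects gives 2.8–3.9. That counts the 4 mg equivalent arm and 10 mg equivalent subjects aged 5–14 on superseded doses, who are outside the comparison anyway.
- **First Part is wrongly built.** SAP 4.1 says the split follows the length of the seamless treatment period, and it counts each period once. That every First Part subject has stopped follows from the definition. One can assume that 25–75% of the non-withdrawers continue and derive First Part withdrawal rates 1.3 to 3.5 times the true rate, but those fractions are not in the documents.

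It also stands that Safety Global by its text covers everyone dosed, that withdrawal reasons are listed and summarised, and that safety listings are given by pattern. Protocol 3.1.3.1 is redacted and the shading in Table 4 is lost, so the rule for ordering stops cannot be checked.

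**Conclusion.** The point holds as a gap in set definition. A first-cohort subject on the final dose or concurrent placebo who withdraws before dose determination is outside both Inferential sets on either reading of pattern a, while the dose-based exclusions do not name that subject and a pattern d counterpart is kept. Table 5 also contradicts the 4.2.2 definition of the Global efficacy population.

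The size is small, 0.3 to 1.5 subjects, resting on constant hazard, the planned cohort sizes and an 8-week First Part. A reader might infer that the primary estimate is biased; the visit schedule does not support that, and the effect on the Vineland-II MMRM is negligible. The consequence is a 10 mg equivalent versus placebo safety comparison that omits early withdrawals from one recruitment block, and some loss on Week 6 or End of Treatment measures. It is firm only for subjects who left before dose determination; those cleared and leaving later can be read as pattern c. The correction is worth making because it is cheap and the omission is tied to outcome.

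**What to change.** 1. In SAP Table 4, limit patterns a and b to stops directed by the IMC/SOC dose decision.
2. Assign first-cohort subjects who stopped for any other reason to the Main Part with pattern c. Include them in both Inferential sets if they were on the final dose for their age or on concurrent placebo. State that subjects cleared to continue who withdraw later remain in c.
3. Align Table 5 with the 4.2.2 text for Efficacy ITT Global.
4. Either label First Part disposition and event rates as conditional on having stopped, or add a supplementary summary of the first 8 weeks of all first-cohort subjects (a, first period of b, and first 8 weeks of c).

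The cost is minor SAP wording and a changed dataset flag that uses withdrawal reasons already recorded. If the supplementary summary is added, pattern c's first 8 weeks appear in two summaries, which are reported separately.
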